### **6.10.4 Specimen Preparation, Testing, Storage, and Shipping**

All specimens collected for this study will be labeled, transported, processed, tested, stored and/or shipped in accordance with SOPs. The frequency of specimen collection and testing will be directed by the Schedule of Evaluations ([Appendix II](#) and [Appendix III](#)).

### **6.10.5 Research Laboratories**

Quantitation of the amount of vaccine virus shed, assays to measure immune responses before and after inoculation, and assessment of nasal washes for adventitious viral agents will be performed at the CIR. Nasosorption assays will be performed at the LID, NIAID. Cytokine/chemokine assays may also be performed on nasal washes from participants infected with vaccine virus if sufficient material is available. Selected specimens may be sent to LID, NIAID for confirmatory testing.

## **6.10.6 Plan for Use and Storage of Biological Samples**

All specimens collected as part of this study may, with the parent/guardian's permission, be stored for future research as part of CIR's approved biospecimen repository for vaccine research. These samples and data may be used for future screening for respiratory virus vaccine studies and to learn more about RSV infection and other diseases. The parent/guardian or child will not own the blood specimens, nasal fluid, or data after it is given to the study. No financial benefit will be provided to the parent/guardian or child from any product or idea created by the investigators using the data or materials. These samples will not be sold or used to make commercial products. Genetic tests will not be performed on these samples unless separate informed consent is obtained.

Samples stored in the repository will be labeled with the study identification number of the participants that, by themselves, cannot identify study participants but are linkable to the study databases generated by the main study. The repository database will contain only the study participants' numbers. A master log linking the study participants' identification numbers to their names is maintained by the study's clinical staff in a password-protected computer system with limited access to authorized research team members and will not be shared with the laboratory. Study participants, or their parents/guardians, may withdraw consent for future testing of their specimens at any time.

## **6.10.7 Biohazard Containment**

As the transmission of blood-borne pathogens can occur through contact with contaminated needles, blood, and blood products, appropriate blood and secretion precautions will be employed by all personnel. The procedures for obtaining, shipping, and handling of all specimens for this study will follow the current recommendation of the Centers for Disease Control and Prevention (CDC) and the NIH. All infectious specimens will be transported using packaging mandated in Title 42 of the Code of Federal Regulations (CFR), Part 72 (42 CFR 72) and in accordance with individual carrier guidelines (e.g., Federal Express).

# **7 SAFETY ASSESSMENT, MONITORING, AND REPORTING**

Participant safety will be carefully assessed, monitored, and reported at multiple levels throughout this study. Sections [7.1-7.4](#) describe safety-related roles, responsibilities, and procedures. The safety monitoring roles of the NIAID Intramural Data Safety and Monitoring Board (DSMB) are briefly referenced in Section [7.1.2](#) and described in detail in Section [9.4.2](#).

## **7.1 SAFETY-RELATED ROLES AND RESPONSIBILITIES**

### **7.1.1 Principal Investigator**

The PI is responsible for continuous monitoring of the CIR's study participants and for alerting the protocol team if unexpected concerns arise. Trained study staff will record safety-related data on CRFs as indicated in Section [7.2](#). The PI is also responsible for prompt reporting to the IRBs and other applicable review bodies of any unanticipated problems (UPs) involving risks to participants or others.

### **7.1.2 Safety Review and Communications Plan (SRCP)**

A Safety Review and Communication Plan (SRCP) was developed for the protocol. The SRCP is an internal communications document between the PI and the IND sponsor (OCRPRO) Clinical Safety Office, which delineates the safety oversight responsibilities of the PI, the CSO, and other stakeholders. The SRCP also includes the overall plan for conducting periodic safety surveillance assessments.

### **7.1.3 Sponsor Medical Monitor**

A medical monitor representing the IND sponsor (OCRPRO) has been appointed for oversight of safety in this clinical study. The sponsor medical monitor will be responsible for performing safety assessments as outlined in a Safety Review and Communications Plan (SRCP).

### **7.1.4 Data Safety Monitoring Board**

An independent DSMB will monitor participant safety through routine and as-needed reviews of study data. Refer to Section [9.4.2](#) for more information on the composition and role of the DSMB in the monitoring of this study.

### **7.1.5 Sponsor Reporting**

A SUSAR is a suspected adverse reaction that is both serious and unexpected, as defined in 21 CFR 312.32. SUSARs will be reported to the FDA and all participating investigators as IND Safety Reports. The Regulatory Sponsor will also submit a brief report of the progress of the investigation to the FDA on an annual basis as defined in 21 CFR 312.33.

Following notification from the PI, OCRPRO, as the IND Sponsor, will report all SAEs to the FDA within the required timelines. Fatal and life-threatening events will be reported within 7 calendar days of the sponsor's awareness and all other SAEs will be reported within 15 calendar days of the sponsor's awareness.

## **7.2 SAFETY-RELATED RECORDING ON CRFs**

AEs that occur during protocol-specified AE reporting periods following inoculation of study product should be considered AEs. The current section outlines which events should be collected on source documents and which should be recorded on CRFs for inclusion in the database.

AEs may be observed by the study investigator or designee, elicited or volunteered from the parent/guardian or participant, or captured on participant's temperature cards. Assessment of safety will include clinical observation and monitoring of laboratory parameters as necessary. Follow-up measures such as history, physical examination, and laboratory testing and/or treatment may be necessary if a participant experiences an AE. Details of AEs will be properly documented on the source documents, recorded on CRFs, and reported to LID investigators and the DSMB in separate semi-annual and annual reports. AEs will be provided to the IRB as defined by the IRB policy.

This study has several periods of AE observation that have different AE CRF recording requirements. In addition, for RSV-seronegative participants, there may be a period when no AEs are recorded on CRFs if the Day 56 Visit occurs in advance of the start of the RSV Season Surveillance Period (November 1). The AEs (solicited and unsolicited; and SAEs) to be recorded on CRFs and the study phase and the calendar dates during which they are to be reported are defined in [Table 19](#) and [Table 20](#).

Concomitant medications and AEs identified in this study will be recorded on CRFs. AEs will be recorded as signs, symptoms, laboratory test results, and diagnoses, as shown in [Table 19](#) and [Table 20](#).

**Table 19: AE CRF Recording Requirements for RSV-Seropositive Subjects**

Study Phase at the Time of Event Onset	Calendar Date	AEs to Record on CRFs	Concomitant Medications to Record on CRFs
Day 0 through midnight of 10 th day following inoculation (Acute Phase)	ANY	
 
• All SAEs
 
• All solicited AEs that meet Appendix IV, criteria
 
• All unsolicited AEs (Grades 1 to 4), with the exception of the following conditions if not treated with prescription medication or non-prescription medications with antipyretic properties: diaper rashes, teething pain, and spitting up
 
	
Record these medications on the CRFs regardless of whether the related event is recorded on the CRFs:
 
 
• All cough and cold remedies including decongestants, cough suppressants, expectorants
 
• All nasal sprays (except saline spray)
 
• All antihistamines
 
• All antipyretics
 
• All prescription medications
 
 
For SAEs and LRIs:
 
 
• All medications related to the recorded event
 

From the 11 th day after inoculation to the 28 th day after inoculation (Post-Acute Phase)	ANY	
 
• All LRIs and SAEs
 
	
 
• All medications related to the recorded event
 

Throughout study	ANY	
 
• Unresolved AEs or SAEs with onset from Day 0 to midnight on the 10th day after inoculation
 
• Unresolved LRIs and SAEs with onset prior to the 28th day following inoculation
 
• 
 
	
 
• All medications related to the recorded event
 

**Table 20: AE CRF Recording Requirements for RSV-Seronegative Subjects**

Study Phase at the Time of Event Onset	Calendar Date	AEs to Record on CRFs	Concomitant Medications to Record on CRFs
Day 0 through midnight of 28 th day following inoculation (Acute Phase)	ANY	
 
• All SAEs
 
• All solicited AEs that meet Appendix IV criteria
 
• All unsolicited AEs (Grades 1 to 4), with the exception of the following conditions if not treated with prescription medication or non-prescription medications with antipyretic properties: diaper rashes, teething pain, and spitting up
 
	
Record these medications on the CRFs regardless of whether the related event is recorded on the CRFs:
 
 
• All cough and cold remedies including decongestants, cough suppressants, expectorants
 
• All nasal sprays (except saline spray)
 
• All antihistamines
 
• All antipyretics
 
• All prescription medications
 
 
For SAEs and LRIs:
 
 
• All medications related to the recorded event
 

From the 29 th day after inoculation to the 56 th day after inoculation (Post-Acute Phase)	ANY	
 
• All SAEs
 
	
 
• All medications related to the recorded event
 

From Day 56 Visit through start of RSV Season Surveillance Period	Up to October 31 in year of inoculation	
 
• Grade <math>\geq 3</math> AEs or SAEs that is deemed related to Pre-RSV Season Study Visit procedures
 
	
 
• All medications related to the recorded event
 

RSV First and Second Season Surveillance Periods	November 1 to March 31	
 
• Fevers, LRIs, URIs, and/or otitis media that are medically attended
 
• All SAEs
 
 
Note: These events do not need to meet the Appendix IV criteria
	
For SAEs and LRIs (all grades):
 
 
• All medications related to the recorded event
 
 
Medications related to recorded medically attended illness should be documented in source notes

Post-RSV Season	Ideally April 1 to April 30; allowable through Sept 30th in the year after the inoculation	
 
• Grade <math>\geq 3</math> AEs or SAEs that are deemed related to Post-RSV Season Study Visit procedures
 
	
 
• All medications related to the recorded event
 

Throughout study	ANY	
 
• Unresolved AEs or SAEs with onset from Day 0 to midnight on the 28th day after inoculation
 
• Unresolved SAEs with onset prior to the 56th day following inoculation
 
• Unresolved SAEs with onset during RSV Surveillance Period or related to the Pre- or Post-RSV Season Study Visit
 
	
 
• All medications related to the recorded event
 

### 7.3 SERIOUS ADVERSE EVENT REPORTING

All SAEs will be reviewed by a study physician, recorded on the Safety Expedited Report Form (SERF) and followed through to resolution. SAEs that have not resolved by the end of the follow-up period are followed until final outcome is known. If it is not possible to obtain a final outcome for an SAE (e.g., the subject is lost to follow-up), the reason a final outcome could not be obtained will be recorded by the investigator on the AE CRF and the SERF. In addition to the SAE Reporting Category identified below, other AEs that must be reported in an expedited manner are LRIs as defined in Appendix IV if they occur during study days 0 to 10 in groups 1 and study days 0 to 28 in group 2.

Deaths and immediately life-threatening SAEs will be reported within 1 business day after the site becomes aware of the event. All other SAEs will be reported within 3 business days of site awareness. SAEs will be reported either by fax or e-mail to all of the following:

- Sponsor: Office of Clinical Research Policy and Regulatory Operations, NIAID, NIH: Clinical Safety Office (CSO): [contact], [contact], [[contact]](mailto:[contact])
- DSMB Executive Secretary: [contact], [contact], [[contact]](mailto:[contact])
- LID, NIAID: [name], NIAID/NIH, [contact], [contact], Email: [[contact]](mailto:[contact])

SAEs will also be reported to WIRB (contact information below) based on its reporting requirements:

- Western Institutional Review Board (WIRB), [name], [contact]

### 7.4 REPORTING OF UNANTICIPATED PROBLEMS TO OCRPRO

An UP is defined as any event, incident, experience, or outcome that is:

1. Unexpected in terms of nature, severity, or frequency in relation to
  - a. The research procedures that are described in the IRB-approved research protocol and informed consent or other study documents; and
  - b. The characteristics of the participant population being studied; and
2. Possibly, probably, or definitely related to participation in the research; and
3. Places participants or others at a greater risk of harm (including physical, psychological, economic, or social harm) than was previously known or recognized. Per the IND sponsor, an AE with a serious outcome will be considered increased risk.

UPs must be reported to the local IRB per their requirements. Non-Serious AEs that are UPs must also be reported to the sponsor CSO. Submit the local IRB UP report form to the CSO at the following address no later than 7 calendar days of the PI awareness of the event.

SPONSOR CLINICAL SAFETY OFFICE CONTACT INFORMATION:

Clinical Safety Office  
[name]  
[name]  
[contact]  
[contact]

UPs that are not AEs (UPnonAE) are not routinely reported to the CSO. However, an UPnonAE that may, in the opinion of the investigator, involve risk to the participant, affect others in the research study, or significantly impact the integrity of research data would be considered a non-serious UP and would be reported to the CSO. For example, we will report occurrences of breaches of confidentiality, accidental destruction of study records, or unaccounted-for study drug.

## **8 PARTICIPANT MANAGEMENT**

### **8.1 MANAGEMENT OF ADVERSE EVENTS**

An AE is any untoward medical occurrence in a participant administered a pharmaceutical product that does not necessarily have a causal relationship with this treatment. An AE can therefore be any unfavorable and unintended sign (including an abnormal laboratory finding), symptom, or disease temporally associated with the subject's participation in the research, whether or not related to the subject's participation in the research. This includes exacerbation of pre-existing conditions and intercurrent illnesses.

Causality assessment is based on available information at the time of the assessment of the AE. The investigator may revise the causality assessment as additional information becomes available.

All AEs identified in this study will be source documented, consistent with the policies and procedures referenced in Section 10. Among other details, source documentation will include the severity of each event (graded as described in Sections 8.2.1 and 8.2.2 and its relationship to study product, assessed by the study clinician according to the following categories and definitions:

**Related** There is a reasonable possibility that the adverse event may be related to the study drug.

**Not related** There is not a reasonable possibility that the adverse event may be related to the study drug.

There are two categories of AEs specific to CIR 322: solicited and unsolicited. Solicited AEs are described in Section 8.1.1. Unsolicited AEs are all other AEs. However, for infants and children, the following common events will not be recorded as AEs unless a prescribed concomitant medication is used to treat them: non-infectious rashes, teething pain, and spitting up. The use of medications will only be captured in the event of an AE or pre-existing condition.

Serious Adverse Events (SAEs) are described in Section 8.1.2.

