### **12.5.5 Receipt of Study Product**

If the study vaccine is insufficiently attenuated, participants could experience rhinorrhea, cough, fever, otitis media, or LRI. Immediate hypersensitivity reactions including urticaria, anaphylaxis, or other immunoglobulin E (IgE)-mediated responses are possible, as with any vaccine. With any investigational vaccine, there is a theoretical possibility of risks about which we have no present knowledge. Parents/guardians will be informed of any such risks should further data become available.

The study participant's family does not pay for the study product or research visits including examinations and laboratory tests that are part of this study, including evaluation of illness, if any. NIAID agrees that the funding for appropriate acute care will be provided through the NIAID

contract (HHS272200900010C) for any side effects that are determined to be related to the administration of vaccine.

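### Section 8.1 and Tables 19/20 set conflicting rules for recording minor AEs and medications; if 8.1 is followed, some non-serious rashes could go unrecorded

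*Combined protocol and SAP*

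**What the plan says.** Section 8.1 divides AEs into solicited and unsolicited, the latter being everything not solicited. It then makes an exception: "However, for infants and children, the following common events will not be recorded as AEs". In full, the rule is that these events "will not be recorded as AEs unless a prescribed concomitant medication is used to treat them: non-infectious rashes, teething pain, and spitting up", so only treatment with a prescribed drug removes the exception. The next sentence limits medication capture to cases with an AE or a condition that was already present.

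Section 7.2 sets out what goes on the CRFs and refers to Tables 19 and 20: "AEs will be recorded as signs, symptoms, laboratory test results, and diagnoses, as shown in" those tables. For the Acute Phase (Days 0-10 in group 1, Days 0-28 in group 2) both tables require all unsolicited AEs of Grades 1 to 4. The exception in Table 20 applies "if not treated with prescription medication or non-prescription medications with antipyretic properties: diaper rashes, teething pain, and spitting up". Table 19 has the same wording. On medications, the tables say: "Record these medications on the CRFs regardless of whether the related event is recorded on the CRFs". The list that follows includes all antihistamines, all antipyretics and all prescription drugs.

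Two other places bear on the point. Section 9.2.1 makes the types and grades of product-related unsolicited AEs a primary safety outcome. Section 12.5.5 warns: "Immediate hypersensitivity reactions including urticaria, anaphylaxis, or other immunoglobulin E (IgE)-mediated responses are possible, as with any vaccine".

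**The concern.** The protocol has two rules for the same recording decision, and they differ on which rashes are exempt, which treatment ends the exemption, and which medications are captured. No section says which rule prevails. The number of unsolicited AEs could therefore depend on which section the staff member applies.

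Rash deserves attention because it is not a solicited event. The solicited list in Section 8.1.1 and Appendix IV covers fever, URI, otitis media and LRI. A non-serious rash can reach the primary safety outcome only as an unsolicited AE, and that is the route Section 8.1 narrows. Section 1.2.3 describes this as the first evaluation of the candidate in humans. The AE frequencies and line listings in Section 9.5.1, and the AE data reviewed by the DSMB under Section 9.4.2, can include only what was recorded.

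**Working it through.** No arithmetic applies, since the contradiction is one of wording. The check applies both rules to the same Acute Phase event.

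| Event and treatment | Section 8.1 | Tables 19/20 |
|---|---|---|
| Non-infectious, non-diaper rash, untreated | Not an AE | Recorded |
| Same rash, over-the-counter antihistamine only | Not an AE | Recorded |
| Teething pain, over-the-counter antipyretic only | Not an AE | Recorded |
| Non-infectious diaper rash, untreated | Not an AE | Exempt |
| Any listed event, prescribed drug | Recorded | Recorded |
| Any event meeting SAE criteria | Recorded as an SAE | Recorded as an SAE |

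1. **Scope.** Rows 1 and 2 differ because 8.1 exempts non-infectious rashes generally, and the tables exempt only diaper rash.
2. **Trigger.** Row 3 differs because 8.1 recognises only a prescribed drug, while the tables also recognise a non-prescription antipyretic. This row needs no judgement about what counts as a rash.
3. **Medications.** In row 2 the tables put the antihistamine on the CRF in any case. Under 8.1 the rash is not an AE, so (absent a pre-existing condition) the antihistamine is not captured either. Following 8.1 throughout would remove the event and also the drug record that might have revealed it.
4. **Severity.** The affected events need not all be Grade 1. Table 21 allows a Grade 2 event to be managed with over-the-counter products after contact with a health care provider, so a Grade 2 rash could fall in row 2.
5. **Urticaria.** For a case to go unrecorded, four conditions must all hold: staff apply 8.1 rather than the tables; they read urticaria as one of the common non-infectious rashes; the case is not serious; and no prescribed drug is given. If any one fails, the case is recorded.
6. **Outcome.** Section 9.2.1 counts product-related events. An omitted rash changes the primary outcome only if it would have been judged related.

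No printed figure in the protocol changes as a result.

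**The case against.** The strongest reply is that the protocol already says which text governs the database. Section 7.2 assigns CRF recording to Tables 19 and 20, and under those tables every acute-phase urticaria is recorded. Section 8.1 belongs to a chapter on participant management. Its exception is limited to common events and names rashes beside teething pain and spitting up, which suggests everyday infant rashes and not acute hypersensitivity. There are other safeguards: SAEs are always recorded (Section 7.3), children are observed for about 30 minutes after inoculation (Table 4), and families are contacted daily through the Acute Phase.

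Much of this stands, and it limits what can be claimed. A reader might infer that urticaria is lost from the primary safety outcome. The documents do not support that: no section classes urticaria as an exempt rash, and the loss needs all four conditions listed above. A reader might also want to size the loss with the detection probabilities in Table 24. That would require an assumed rash rate made up wholly of non-diaper events that 8.1 excludes, so the contrast with zero would be true by construction.

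The reply does not remove the contradiction. Section 7.2 designates the tables but does not say that they override 8.1. Section 8.1 also acts first, because it decides what counts as a recordable AE before a table listing unsolicited AEs is consulted. The word common is not defined, so whether a given rash is exempt is left to individual judgement. Daily contact may leave a note of the rash in source documents, but a source note does not enter the analysis dataset.

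**Conclusion.** The contradiction is certain and has three parts: the exempt rashes, the treatment that ends the exemption, and the medications captured. The consequence is conditional. If Section 8.1 is followed, non-serious non-diaper rash that is untreated or treated only with over-the-counter drugs could go unrecorded. Such rash may include urticaria, and any product-related case would be missing from the primary unsolicited-AE outcome. If Tables 19 and 20 are followed, none of these cases is lost. Serious or prescription-treated cases are recorded under both rules.

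The size cannot be estimated, because the documents give neither a rash rate nor the share of such events that staff would leave out under 8.1. This is an inconsistency in data recording, not a fault in the analysis methods of Section 9.5. It should be corrected because it bears on a primary outcome and the correction is small.

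**What to change.** Reconcile the passages so that Section 7.2 and Tables 19/20 govern:

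- In Section 8.1, replace the exemption sentence with the content of the tables: diaper rash, teething pain and spitting up are exempt, and the exemption ends if a prescription drug or an over-the-counter antipyretic is used.
- Delete the Section 8.1 sentence on medication capture, so that the medication columns of Tables 19 and 20 apply.

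The cost is two sentences of text and a few more minor AEs on the CRFs. Sample size, visits and analysis methods do not change.
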